## 8.2 Secondary Objectives

There are two secondary objectives for this study.

- a) The first secondary objective (**SO-1**) is to compare the clinical importance of apneic events in a 48-hour monitoring period after vaccination in the “vaccinated” group versus a 48-hour monitoring period after randomization in the “unvaccinated” group.

There are 3 secondary outcome measures (SOM) for this objective. For SOM 1.1, the average number of apnea events in each group will be presented and the number of apnea events will be compared using a Poisson regression model with study site and gestational age as covariates to control for the randomization blocks. Summary statistics regarding the number of distinct apnea episodes and the duration of episodes, including mean, median, standard deviation, and range will be reported by group and site.

For SOM 1.2, the average duration of apnea episodes between groups will be compared using a mixed effects model (Robinson 2007) with a random intercept for each infant with one or more events and study site and gestational age as covariates to control for the randomization blocks. Apneic events will be identified using the same criteria for primary objective.

For SOM 1.3, the proportion of infants requiring an increase in respiratory support will be presented and compared using a Mantel-Haenszel statistic in a stratified analysis by site and gestational age to control for the randomization blocks at the two-sided  $\alpha 0.05$  level. The stratified odds ratio and corresponding 95% confidence interval for the occurrence will also be calculated. These tests will be performed at the  $\alpha 0.05$  level.

Increase in mode of respiratory support will be defined as (a) progression from any lower level at baseline (at time of randomization in the unvaccinated group and vaccination in the vaccinated group) to any higher level, as well as (b) any increase in nasal cannula flow rate, or continuous positive airway pressure (CPAP).

- b) The subsequent secondary objective (**SO-2**) is to compare proportions of preterm infants with severe cardiorespiratory events in a 48-hour monitoring period after vaccination in the “vaccinated” group versus a 48-hour monitoring period after randomization in the “unvaccinated” group.

For this objective the proportion of infants in each group who experienced  $\geq 1$  severe cardiorespiratory event (SOM 2.1, as defined in **Section 5.4**) or received positive pressure ventilation (SOM 2.2) at least once during the 48 hours after

randomization/vaccination will be presented and these proportions will be compared using a Mantel-Haenszel statistic in a stratified analysis by study site and gestational age to control for the randomization blocks. The stratified odds ratio and corresponding 95% confidence interval for the occurrence of both measures will also be calculated.

Severe cardiorespiratory events will be defined according to the protocol. Events that meet the protocol-defined criteria due *only* to a respiratory pause of >30 seconds will be confirmed by manual review. Only events confirmed by manual review will be counted. However, events without supporting cardiorespiratory monitoring strips, that cannot be manually reviewed, will also be counted as apnea for this analysis.

No adjustments will be made to the alpha level (two-sided  $\alpha=0.05$ ) for these secondary objectives.

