The perceived risk of reappearance or worsening of apnea after vaccination in premature infants likely contributes to undervaccination. Apnea is a common symptom noted in the NICU in the presence or absence of vaccination due to apnea of prematurity. Apnea of prematurity is a developmental disorder characterized by cessation of breathing and often accompanied by bradycardia, cyanosis, or pallor. Apneic events can be divided into 3 subtypes: central (failure of the infant to initiate a breath; obstructive (related to pharyngeal obstruction); and mixed (combination of central and obstructive). The pathogenesis of apnea of prematurity involves persistence of immature reflexes and immature responses to hypoxia and hypercapnia. The incidence of apnea is inversely proportional to the gestational age (GA) at birth, with essentially all infants ≤ 28 weeks' gestation diagnosed with apnea and 20% of those born at 34 weeks' gestation.¹¹ Most, but not all, of the U.S. Food and Drug Administration labels for the commonly administered infant vaccines mention premature infants (**Table 1**). While none of the vaccinations are specifically indicated in premature infants, several labels provide warnings that advise of the risk of apnea following vaccination in premature infants (**Table 1**). Awareness of this potential risk has originated from a number of retrospective and observational studies that have evaluated vaccination safety in premature infants (**Table 2**). The incidence of cardiorespiratory events (i.e. apnea and/or bradycardia) following vaccination ranged from 0-47% in these studies. Risk factors for cardiorespiratory events in some studies included lower gestational age and higher clinical disease severity (such as longer period of ventilation and presence of chronic lung disease). In several of these studies, infants served as their own controls, as they were observed pre-vaccination.

The relationship between vaccination and apnea has been studied extensively but the evidence is inconclusive for a causal association. While retrospective and prospective observational studies suggest a possible link between vaccination and apnea in premature infants, there are several inherent problems with these studies. Each study examines different

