6.2.2.3 Final study analysis

A final analysis of the data will occur after all infants have completed the study and will include data from infants enrolled in the pilot study.

All proportions specified below in the objectives will be compared by group (unvaccinated group or vaccinated group) using a Mantel-Haenszel statistic in a stratified analysis by site (i.e. Duke, UNC and CCHMC) to control for the randomization blocks at the two-sided alpha 0.05 level unless otherwise specified. The odds ratio and corresponding 95% confidence interval will also be calculated and presented. There will be no adjustment to the alpha level made for the secondary and exploratory objectives.

Primary Objective 1 - To compare proportions of preterm infants with apnea in a 48-hour monitoring period after vaccination in the “vaccinated” group versus a 48-hour monitoring period after randomization in the “unvaccinated” group.

The proportion of infants with ≥ 1 apneic event apnea (as defined in Section A.5.3) will be presented for each group and compared using a Mantel-Haenszel statistic.

Secondary Objective 1 - To compare the clinical importance of apneic events in a 48-hour monitoring period after vaccination in the “vaccinated” group versus a 48-hour monitoring period after randomization in the “unvaccinated” group.

For this objective we will present the proportions of infants in each group who required increase in respiratory support (as defined in Section A.5.3) and compare these proportions using a Mantel-Haenszel statistic. We will also report summary statistics regarding the number of distinct episodes and the duration of episodes, including mean, median, standard deviation, interquartile range, and range. We will compare the number of distinct episodes of apnea and the duration of episodes between groups using the Wilcoxon rank sum test.

Secondary Objective 2 - To compare proportions of preterm infants with severe cardiorespiratory events in a 48-hour monitoring period after vaccination in the “vaccinated” group versus a 48-hour monitoring period after randomization in the “unvaccinated” group.

For this objective we will present the proportion of infants in each group experiencing a severe cardiorespiratory event (as defined in Section A.5.3) or received positive pressure ventilation at least once during the 48 hours after randomization/vaccination and compare these proportions using a Mantel-Haenszel statistic.

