### 8.3 Exploratory Objectives

There are three exploratory objectives for this study.

- a) The first exploratory objective (**EO-1**) is to compare proportions of preterm infants with temperature instability in a 48-hour monitoring period after vaccination in the “vaccinated” group versus a 48-hour monitoring period after randomization in the “unvaccinated” group.

For this objective we will present the proportion of infants in each group experiencing fever (temperature  $\geq 38^{\circ}\text{C}$ ) (EOM 1.1) and the proportion in each group experiencing hypothermia (temperature  $< 36^{\circ}\text{C}$ ; as defined in **Section 5.4**) (EOM 1.2) at least once during the 48 hours after randomization/vaccination. These proportions (fever and hypothermia) will be compared using a Mantel-Haenszel statistic in a stratified analysis by study site and gestational age to control for the randomization blocks. The stratified odds ratio and corresponding 95% confidence interval for the occurrence of fever and hypothermia will also be calculated.

- b) The second exploratory objective (**EO-2**) is to compare event counts and proportions of preterm infants with other clinically important adverse events in a 48-hour monitoring period after vaccination in the “vaccinated” group versus a 48-hour monitoring period after randomization in the “unvaccinated” group.

For this objective the number of oxygen desaturation events (EOM 2.1) and the number of bradycardia events (EOM 2.2) will be presented using summary statistics regarding the number of distinct events and the duration of events, including mean, median, standard deviation, and range will be reported by group and site. The number of events for each outcome will be compared using a Poisson regression model with study site and gestational age as covariates to control for the randomization blocks.

The proportion of infants in each group experiencing other clinically important adverse events (infants requiring blood culture and/or antibiotics (intravenously or intramuscularly) in the setting of blood culture for sepsis evaluation (EOM 2.3) and infants with a serious adverse event (SAE; EOM 2.4; protocol section 5.4) at least once during the 48 hours after randomization/vaccination will be presented. These

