proportions will be compared using a Mantel-Haenszel statistic in a stratified analysis by study site and gestational age to control for the randomization blocks. The stratified odds ratio and corresponding 95% confidence interval for the occurrence of these outcome measures will also be calculated. We will provide a listing of SAE narratives and relatedness descriptions.

- c) The third exploratory objective (**EO-3**) is to compare clinically important adverse events occurring between 48 hours and 14 days after vaccination among infants in the vaccinated group who do / do not have apnea in a 48-hour monitoring period after vaccination.

For this objective the proportion of infants in the vaccinated group with and without apnea in a 48-hour monitoring period who experience each of the clinically important adverse events listed below at least once between 48 hours and 14 days after vaccination will be presented.

- $\geq 1$  episode of clinical apnea in hospitalized infants (EOM 3.1)
- any increase in respiratory support in hospitalized infants (EOM3.2)
- blood culture and/or antibiotics (intravenously or intramuscularly) in the setting of blood culture for sepsis evaluation in hospitalized infants (EOM 3.3)
- positive pressure ventilation in hospitalized infants (EOM 3.4)
- readmission to the hospital within 14 days of vaccination in discharged infants (EOM 3.5)

These subgroup comparisons will be made using a Mantel-Haenszel statistic in a stratified analysis by study site and gestational age to control for the randomization blocks at the two-sided alpha 0.05 level. The stratified odds ratio and corresponding 95% confidence interval for the occurrence of these outcome measures will also be calculated.

No adjustments will be made to the alpha level (two-sided alpha=0.05) for these exploratory analyses.

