#### **8.4 Postmenstrual age (PMA) Evaluation**

Study objectives PO1, SO1, SO2, EO2.1, EO2.2, EO3.1, and EO3.2 will be presented and evaluated between groups by postmenstrual age group (PMA <37 weeks /  $\geq$ 37 weeks). PMA will be defined as the sum of gestational age plus postnatal age. PO1, SO2, and EO3 are categorical with either no event or 1 or more events, and will be presented and compared using a Mantel- Haenszel statistic by PMA group at the two-sided alpha 0.05 level. The stratified odds ratio and corresponding 95% confidence interval for the occurrence will also be calculated. SO1 and EO2 are count data and will be compared using a Poisson regression model with study site as covariates by PMA group. These tests will be performed at the alpha 0.05 level.

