## **9 SENSITIVITY ANALYSES**

The following sensitivity analyses are planned:

- 1) Apneic events that cannot be adjudicated will be counted as non-apneic events, and the PO-1 and SO-2 (severe cardiorespiratory events) will be reanalyzed.
- 2) All apneic events determined by the cardiorespiratory monitor will be counted as apneic events, regardless of manual review, and the PO-1 and SO-2 (severe cardiorespiratory events) will be reanalyzed.
- 3) The following infants will be excluded from analysis and all objectives re-analyzed:
  - a. Infants with a major surgical procedure (including circumcision) during the study period.
  - b. Receipt of any intramuscular injection, including Synagis or a vaccine other than DTaP, IPV, HBV, PCV13, or Hib during the study period.

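### SAP 8.2 to 8.4 test per-infant event counts by Poisson regression with no stated allowance for overdispersion, so p-values are too small if infants differ beyond site and gestational age

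*SAP*

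**What the plan says.** SAP 8.2 states for SOM 1.1 that "the number of apnea events will be compared using a Poisson regression model with study site and gestational age as covariates". SAP 8.3 states for EOM 2.1 (desaturation) and EOM 2.2 (bradycardia): "The number of events for each outcome will be compared using a Poisson regression model with study site and gestational age as covariates". SAP 8.4 then says that "SO1 and EO2 are count data and will be compared using a Poisson regression model with study site as covariates by PMA group", with gestational age no longer in the model.

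These tests are at two-sided 0.05 without multiplicity adjustment; for 8.3 the text is "No adjustments will be made to the alpha level (two-sided alpha=0.05) for these exploratory analyses". The list in SAP 9 that opens "The following sensitivity analyses are planned" changes which events count or which infants are included. No item changes the variance assumption. SAP 8.2 and 8.3 do ask for standard deviations of the counts, which would reveal overdispersion, but nothing says what would then happen to the test. For apnea duration (SOM 1.2), by contrast, SAP 8.2 includes a random intercept per infant.

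Protocol 6.2.2.3 prescribes something else for apnea: "We will compare the number of distinct episodes of apnea and the duration of episodes between groups using the Wilcoxon rank sum test". For Exploratory Objective 2 it gives Mantel-Haenszel comparisons of the proportion of infants with at least one event.

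**The concern.** Each infant contributes one count. Model-based Poisson standard errors are right only if, within site and gestational age, the variance of that count equals its mean. Protocol 1.1 gives reason to doubt this: "Risk factors for cardiorespiratory events in some studies included lower gestational age and higher clinical disease severity". Gestational age is in the 8.2 and 8.3 models, but severity is in none of them. If some infants are prone to repeated events and most have none, the variance exceeds the mean, the standard error is too small and so is the p-value.

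A chance imbalance in either direction could then be declared significant. The main exposure is SOM 1.1, the first listed measure of how clinically important the apneas are. A false finding of more, or fewer, apneas after vaccination would bear on the question the trial was set up to inform. Rate-ratio standard errors, if reported later, would be too small in the same way; the SAP plans no interval for a Poisson analysis.

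**Working it through.** **The plan's own figure.** The only stated power figure is for the primary endpoint: 15% v 30%, 135 per group, two-sided 0.05, chi-square (SAP 4.2). With pooled p = 0.225, SE0 = √(2×0.225×0.775/135) = 0.0508 and SE1 = √((0.15×0.85 + 0.30×0.70)/135) = 0.0500. Power = Φ((0.15 − 1.96×0.0508)/0.0500) = 84.3%, as stated, and 270/0.9 = 300. No mean, variance or power is given for any count.

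**Inputs from the documents.** 300 infants; site totals 90/90/120 (protocol 3: 4+86, 4+86, 4+116); 1:1 allocation; 15% of infants with at least one apnea (the unvaccinated figure, used for both arms because the simulations have no vaccine effect).

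**Assumptions.** Two equal gestational-age strata, with 15/15, 20/10 or 25/5% affected; negative binomial counts with shape k; event means, between-infant CVs and subgroup sizes as shown below.

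**Step 1: large-sample formula.** If variance = φ × mean, the true size of a nominal 5% model-based test is 2×(1 − Φ(1.96/√φ)). For a negative binomial, φ = 1 + mean/k. A pure Poisson law with 15% affected (15/15) has mean −ln(0.85) = 0.1625, which is 0.1625/0.15 = 1.08 apneas per affected infant. Solving k for 1.2, 2 and 5 apneas per affected infant gives:

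| Apneas per affected infant | k | φ | True size |
|---|---|---|---|
| 1.2 | 0.809 | 1.22 | 7.6% |
| 2 | 0.145 | 3.07 | 26.3% |
| 5 | 0.064 | 12.75 | 58.3% |

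**Step 2: simulation of the 8.2 model** (arm, site, gestational age; 4000 trials per setting). Rejection rates in %, in the order no overdispersion / 1.2 / 2 / 5 apneas per affected infant:

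| Affected by stratum | Model-based | Pearson-scaled | Robust (HC1) |
|---|---|---|---|
| 15/15% | 5.2 / 6.9 / 26.6 / 58.8 | 5.3 / 4.4 / 6.1 / 7.5 | 5.3 / 4.7 / 6.3 / 8.2 |
| 20/10% | 5.4 / 7.4 / 26.6 / 60.8 | 5.5 / 5.5 / 7.1 / 12.7 | 5.4 / 5.4 / 6.4 / 9.2 |
| 25/5% | 4.6 / 6.3 / 24.6 / 58.4 | 5.0 / 5.7 / 9.0 / 15.9 | 4.8 / 5.2 / 5.9 / 8.1 |

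The Monte Carlo standard error at 5% is √(0.05×0.95/4000) = 0.34 points.

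**Step 3: more frequent events, as in 8.3** (3000 trials; k = 1/CV², so φ = 1 + mean × CV²). Model-based size in %, at CV 0.25 / 0.5 / 1.0:

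| Stratum means | Model-based size |
|---|---|
| 5/5 | 8.5 / 19.1 / 42.7 |
| 8/2 | 10.4 / 24.6 / 48.7 |
| 20/20 | 19.5 / 39.7 / 67.5 |
| 32/8 | 22.2 / 47.7 / 71.6 |

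As a check, mean 5 with CV 0.5 gives φ = 2.25 and 2×(1 − Φ(1.96/1.5)) = 19.1%. Over all these settings robust errors gave 4.1% to 5.9% and Pearson-scaled 4.6% to 9.3%.

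**Step 4: the 8.4 model** (site only; assumed subgroups of 75, 150 and 225; 15/15 and 25/5; 3000 trials each). Model-based size was 3.3% to 7.8%, 21.4% to 26.4% and 55.5% to 59.7% at 1.2, 2 and 5 apneas per affected infant. Pearson-scaled errors gave 2.3% to 6.8%. Robust errors reached 14.0%, 10.5% and 8.7% in subgroups of 75, 150 and 225.

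**Step 5: second simulation** (270 infants, 15% to 30% affected, k from 2 down to 0.2). The model-based size ran from 5.3% to 43.8%; Pearson-scaled and robust errors stayed between 4.2% and 7.7%.

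**The case against.** The SAP is silent rather than wrong. It names a model but no variance estimator, and robust or scaled errors would not contradict it. That is true, but the ordinary reading of an unqualified Poisson regression is model-based errors, and choosing the estimator after seeing the counts is what a SAP should prevent.

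The size rests entirely on assumptions. The documents do not favour 2 or 5 apneas per affected infant over 1.2, where inflation is only about 1 to 2.5 points. Severity is cited as a risk factor only in some studies, and protocol 4.2 narrows the range by excluding infants on mechanical ventilation or NIPPV and those with active infection under treatment. This stands: the larger figures are not predictions. Variation beyond site and gestational age remains likely, but its degree is unknown.

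The reach is limited, with one secondary measure mainly exposed. This also stands; for the exploratory measures and 8.4 the point is a clarification.

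On Exploratory Objective 2, protocol 2.1 defines EOM 2.1 and 2.2 as average numbers of events, which the SAP's count model fits better than the at-least-once proportions in protocol 6.2.2.3. So that mismatch lies partly within the protocol. It still has to be resolved, and the conflict over apnea number and duration is plain.

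The choice of estimator by section depends on assumed subgroup sizes. It is a preference, not a condition of the fix.

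**Conclusion.** The concern holds. As ordinarily read, SAP 8.2 to 8.4 give p-values that are too small for SOM 1.1, EOM 2.1, EOM 2.2 and their postmenstrual-age repeats whenever infants differ beyond the modelled covariates, and the protocol's background makes such differences likely. The amount is conditional: slight if nearly every affected infant has a single apnea, several-fold if a few infants carry most events or if mean counts are high. With no overdispersion the planned test is sound (4.6% to 5.4%). The case for change is that the correction costs almost nothing if counts are Poisson and removes most of the inflation if they are not. It should be fixed before the count analyses are run. Separately, and whatever the dispersion, the protocol and SAP prescribe different tests for apnea number and duration and for Exploratory Objective 2.

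**What to change.** Add one sentence to each of SAP 8.2, 8.3 and 8.4: the Poisson models keep their planned covariates and use robust (sandwich) or Pearson-scaled (quasi-Poisson) standard errors. Either is acceptable. If one is named per section, robust errors suit 8.2 and 8.3: Pearson scaling assumes one dispersion across gestational-age strata, while protocol 1.1 says that "The incidence of apnea is inversely proportional to the gestational age (GA) at birth". Pearson-scaled errors suit 8.4, where groups are smaller and gestational age is not in the model.

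Reconcile the SAP with protocol 6.2.2.3 for apnea number and duration and for Exploratory Objective 2, stating which test governs. A supporting rank test for SOM 1.1 is optional.

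The cost is three sentences and one option in models already planned, with no new data. The downsides are less favourable p-values when counts are overdispersed and some residual inflation when few infants carry most events. With robust errors this was up to about 9% overall in these simulations, and about 10% or 14% in an assumed subgroup of 150 or 75 if robust errors are used there.

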4.4 Reasons for and Handling of Withdrawals

The following may be reasons for study withdrawal:

- As deemed necessary by the principal investigator (PI).
- Parent(s)/LAR(s) withdrawal of permission for their infant to participate.
- Loss to follow-up.
- Termination of the study by the sponsor.

A parent/LAR may withdraw permission for their infant to participate at any time and for any reason, without penalty. Subjects who are withdrawn from the study prior to randomization will be replaced. Subjects who are withdrawn from the study after randomization will not be replaced. For subjects who were randomized, data collected prior to withdrawal from the study will be included in the study.

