 - a. *Definition:* Increase in mode of respiratory support will be defined as progression from any lower level at baseline (at time of randomization in the unvaccinated group and vaccination in the vaccinated group) to any higher level (**Figure 2**). In addition, any increase in nasal cannula flow rate, or continuous positive airway pressure (CPAP) will be considered an increase in mode of respiratory support.
 - b. *Method of collection:* Respiratory data will be collected from the EHR daily, and the highest level of support that is maintained for >1 hour will be recorded. In addition, start/stop date/time for NIPPV and mechanical ventilation will be recorded.
 3. Severe cardiorespiratory event (SOM 2.1)
 - a. *Definition:* Respiratory pause of >30 seconds in duration or bradycardia of <60 beats per minute for >10 seconds
 - b. *Method of collection:* Obtained from the cardiorespiratory monitor as described above.
 4. Positive pressure ventilation delivered via bag-valve mask (SOM 2.2)
 - a. *Definition:* Infant with unexpected clinical decompensation requiring positive pressure ventilation via bag-valve mask.
 - b. *Method of collection:* Obtained from the EHR as documented by a clinical provider (e.g., physician, nurse, respiratory therapist).
 5. Fever (EOM 1.1)
 - a. *Definition:* Elevated temperature $\geq 38^{\circ}\text{C}$.
 - b. *Method of collection:* Highest daily temperature will be recorded from the EHR, in addition to how the temperature was obtained (skin, axillary, rectal, etc.) and infant's environment (open crib, radiant warmer or isolette).
 6. Hypothermia (EOM 1.2)
 - a. *Definition:* Decreased temperature $< 36^{\circ}\text{C}$.
 - b. *Method of collection:* Lowest daily temperature will be recorded from the EHR, in addition to how the temperature was obtained (skin, axillary, rectal, etc.) and infant's environment (open crib, radiant warmer or isolette).
 7. Oxygen desaturation (EOM 2.1)
 - a. *Definition:* Oxygen desaturation will be defined as a $\text{SpO}_2 < 88\%$ for >10 seconds.
 - b. *Method of collection:* Obtained from the cardiorespiratory monitor as described above.
 8. Bradycardia (EOM 2.2)
 - a. *Definition:* Bradycardia will be defined as a heart rate <80 beats per minute lasting >10 seconds.

- b. *Method of collection*: Obtained from the cardiorespiratory monitor as described above.
- 9. Blood culture for sepsis evaluation (*EOM 2.3*)

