**Figure 1. Intent-to-Treat (ITT) Analysis**

**6.2 Modified Intent-to-Treat (mITT) population (Figure 2)**

- a) **Definition:** The definition is the same for the ITT and mITT. The mITT population includes any infant that was enrolled and randomized in the study.
- b) **Analysis:** For the mITT analysis, infants will be analyzed in their assigned treatment arms irrespective of receipt of vaccine. Study outcomes will be included in the analysis as follows:
  - i) **Vaccinated group:** study outcomes in the 48-hour monitoring after vaccination. If vaccination does not occur by 12 hours after randomization, then study outcomes will be assessed between 12 and 60 hours after randomization.
  - ii) **Unvaccinated group:** study outcomes in the 48-hour monitoring period after randomization. This is the same for the IIT and the mITT populations.

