## 6.4 Analysis of populations

The mITT population will be the primary analysis population for all planned analyses for the study objectives. The ITT population will be analyzed for the primary objective. The PP population will be analyzed for all planned objectives as supporting analyses. For comparison, pre-specified secondary analyses will also be performed using the ITT and PP populations.

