### Major Protocol Violations for Analysis

1. Infant later found to have not met inclusion/exclusion criteria at the time of study entry.
  - a. Infant will not be counted as a protocol violation for analysis if the only exclusion criterion met is that the child or parent/LAR is an immediate relative of study staff or an employee who is supervised by study staff.
2. Infant did not have cardiorespiratory monitoring data for the fully specified time period after vaccination/randomization
  - a. Vaccinated group: No cardiopulmonary data for 48 or more hours after vaccination. Infants with <1 hour of absent cardiopulmonary data for this period will not be considered a violation for analysis.
  - b. Unvaccinated group: No cardiopulmonary data for 48 or more hours after randomization. Infants with <1 hour of absent cardiopulmonary data for this period will not be considered a violation for analysis.
3. Infant did not receive all vaccines by 12 hours after randomization in the vaccinated group
4. Infant in the unvaccinated group received vaccines during the 48 hours after randomization.

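### The Poisson count models have no term for monitored time, so unequal monitoring loss between arms would bias the count ratios for apnea, desaturation and bradycardia

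*SAP*

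**What the plan says.** Three places in the SAP specify count models.

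- SAP 8.2 (SOM 1.1, apnea): "the number of apnea events will be compared using a Poisson regression model with study site and gestational age as covariates".
- SAP 8.3(b) (EOM 2.1 desaturation, EOM 2.2 bradycardia): "The number of events for each outcome will be compared using a Poisson regression model with study site and gestational age as covariates".
- SAP 8.4 (by postmenstrual age): "SO1 and EO2 are count data and will be compared using a Poisson regression model with study site as covariates by PMA group".

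None names an offset, a rate denominator, a minimum monitored time or a rule for lost hours. The sensitivity analyses in SAP 9 do not cover short observation. For the number of apneic episodes, Protocol 6.2.2.3 names a Wilcoxon rank sum test instead, which ignores monitored time as well.

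On who is analysed, SAP 6.2 says "The mITT population includes any infant that was enrolled and randomized in the study", and SAP 6.4 says "The mITT population will be the primary analysis population for all planned analyses for the study objectives". Protocol 4.4 keeps the data recorded before a withdrawal and adds: "Subjects who are withdrawn from the study after randomization will not be replaced".

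Monitoring completeness matters only for the per-protocol (PP) set. SAP Appendix 1 item 2 makes incomplete monitoring a major violation, with this tolerance: "Infants with <1 hour of absent cardiopulmonary data for this period will not be considered a violation for analysis". SAP 7.2 also has the flow chart report how many infants have complete monitoring data.

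**The concern.** A Poisson model of raw counts without an offset gives every infant the same exposure. Three apneas in 12 recorded hours then count the same as three in 48. That is harmless when nearly everyone is monitored for the full window, or when both arms lose time alike. It is not harmless when one arm loses more, because the lost hours enter as if they were free of events.

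SOM 1.1 is one of the measures meant to show how clinically important apnea is after vaccination. The trial is open-label, so withdrawal could depend on assignment. The mITT window also starts later in the vaccinated arm: at vaccination, or at 12 hours after randomization if no vaccine has been given. The same loss time can therefore cost that arm more. If monitoring stops 48 hours after randomization, a control has 48 of 48 window hours, an infant vaccinated at 6 hours has 48 − 6 = 42, and one vaccinated at 12 hours has 48 − 12 = 36. These are ways in which a difference could arise, not evidence that it will.

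**Working it through.** **The plan's own figures.** The documents give no power or precision figure for the counts. The stated power concerns the binary primary endpoint, and it reproduces. With 135 per group, 15% versus 30% and two-sided alpha 0.05:

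z = [0.15·√135 − 1.96·√(2·0.225·0.775)] / √(0.15·0.85 + 0.30·0.70) = (1.743 − 1.157)/0.581 = 1.008, which gives 84.3%.

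The dropout allowance reproduces too: 270/0.90 = 300. This 10% serves only to set the sample size. It is not given by arm and is not tied to the 48-hour window.

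**Formula.** Let f be the share of infants in an arm with truncated monitoring, L the fraction of the 48 hours that they lose, and k their event rate relative to other infants. With equal rates otherwise, the model without an offset estimates

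ratio = [(1 − f_v) + f_v·k·(1 − L)] / [(1 − f_c) + f_c·k·(1 − L)],

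where v is vaccinated and c unvaccinated. All values of f, L and k below are assumptions.

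**Loss unrelated to event rate (k = 1, true ratio 1.00), 12 of 48 hours observed (L = 0.75):**

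- 10% vs 3%: (0.90 + 0.10·0.25)/(0.97 + 0.03·0.25) = 0.925/0.9775 = 0.946
- 10% vs 0%: 0.925/1.000 = 0.925
- 5% vs 2%: 0.9625/0.985 = 0.977
- 3% vs 10% (split reversed): 0.9775/0.925 = 1.057
- 10% in both arms: ratio 1.00, but each arm's mean count is 0.925 of its full-window value, so 7.5% low

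**Same, with half the window lost (L = 0.5):** 5% vs 2% gives 0.975/0.99 = 0.985; 10% vs 2% gives 0.95/0.99 = 0.960; 20% vs 0% gives 0.90.

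For 10% vs 2%, a simulation of 300 trials (150 infants per arm, Poisson regression with site and gestational age) gave 0.967 without an offset and 1.008 with one. The Monte Carlo standard error was about 0.006.

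**Loss concentrated in high-rate infants (10% vs 2%, L = 0.5).** With an offset, each arm's mean count is divided by its mean monitored fraction, here 0.95 and 0.99.

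| k | Full-window ratio | No offset | With offset |
|---|---|---|---|
| 3 | 1.20/1.04 = 1.154 | 1.05/1.01 = 1.040 | (1.05/0.95)/(1.01/0.99) = 1.083 |
| 5 | 1.40/1.08 = 1.296 | 1.15/1.03 = 1.117 | (1.15/0.95)/(1.03/0.99) = 1.164 |

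The offset recovers (1.083 − 1.040)/(1.154 − 1.040) ≈ 38% of the gap at k = 3, and (1.164 − 1.117)/(1.296 − 1.117) ≈ 26% at k = 5.

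**The case against.** The SAP is silent on an offset; it does not rule one out. A count model without one is ordinary for a fixed 48-hour window. The design also limits early loss: infants planned for discharge within 60 hours are ineligible (Protocol 4.1), major procedures expected within 60 hours exclude the infant or delay randomization (Protocol 4.2), and monitoring is inpatient standard of care. Some of the 10% dropout could fall in the vaccinated arm's follow-up to day 14, after the window. The pilot target of 80% with the full 48 hours assessed is a feasibility benchmark for 12 infants. All this stands, and it means that a difference between arms is possible but not shown.

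The bias is also small against sampling error. Assume 15% of infants with apnea in both arms, 135 per arm and simple Poisson counts. The mean is then −ln(0.85) = 0.163, or about 22 events per arm, so SE(log ratio) ≈ √(2/22) ≈ 0.30. Since ln(0.946) = −0.056, the bias is about 0.2 standard errors. That limits the priority of the point, but is no reason to leave exposure out.

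The PP analysis does check the withdrawal route, but only as support, and it drops infants with an hour or more of absent data instead of using their recorded hours.

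A reader might go further on ventilation. Mechanical ventilation is an entry exclusion, no rule covers ventilation that starts inside the window, and "start/stop date/time for NIPPV and mechanical ventilation will be recorded". It is tempting to conclude that ventilated hours enter as event-free time, so that the sickest infants get the lowest counts. The documents do not say that the monitor detects no apnea during ventilation; that is a clinical premise from outside them. A move to ventilation should also appear as harm under SOM 1.3, within the same objective.

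**Conclusion.** The point holds as a gap in specification for one secondary and two exploratory measures. Followed as written, the primary mITT count models give partly monitored infants full exposure. The count ratio is then biased downward for whichever arm loses more monitored time. Under the assumed splits with 12 of 48 hours observed, a null ratio reads 0.925 to 0.977 when the vaccinated arm loses more, and above 1 when the split is reversed. With balanced loss there is no bias in the ratio, only understated mean counts.

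The documents do not support the inference that harm from vaccination will be hidden. They give no truncation rates by arm, no reason to place the 10% dropout in the vaccinated arm or inside the window, and no statement about apnea detection during ventilation. The binary primary endpoint is not part of this point.

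**What to change.** In SAP 8.2, 8.3(b) and 8.4, add log(valid monitored hours in the analysis window) as an offset to each count model. Report monitored hours and events per 24 monitored hours by arm. State what happens to an infant with no valid hours in the window, for whom the logarithm is undefined; a count by arm is enough.

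Reporting ventilated hours by arm alongside SOM 1.3 is reasonable. Subtracting them from exposure should be at most a sensitivity analysis, because it changes the estimand from episodes in a 48-hour period to a rate while not ventilated.

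The cost is one model term and a short table. Monitored hours must already be determined for Appendix 1 item 2, and ventilation times are already collected. The downside is that an offset assumes the event rate in the lost hours equals that in the recorded ones. If truncated infants have higher rates, it removes only part of the bias, so the hours by arm need to be read with the ratio.
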